9.3.2. Outcomes

When available, the following variables will be collected after initiation of Mysimba/Contrave (Post-Index Date). A draft listing of variables available in each country is included in Appendix 3 and will be included as final in the Statistical Analysis Plan (SAP).

Proprietary and Confidential:

This document cannot be used, distributed, or reproduced in any way without the prior written consent of Currax Pharmaceuticals LLC.

- 1. BMI, height, and weight prior to index date, the date of initiation of the medication(s) of interest, (obtained directly from data sources; BMI may be calculated if height and weight available). In the event that BMI and/or weight are not available through licensed access to the Scandinavian National Patient Registries, an attempt will be made to identify the obese population through diagnosis codes or procedures such as counseling for weight loss. It should be noted that this approach may identify a more obese and more motivated population than what would be identified on the basis of BMI. In addition, an approach may be implemented to predict BMI or apply published algorithms predicting BMI. Details will be laid out in the SAP.
- 2. Weight will be obtained if available 16-24 weeks post-index date to evaluate use inconsistent with labelled indication. BMI after index date will be obtained in the same timeframe, if available.
- 3. Relevant comorbidities (obtained via ICD-10 codes):
 - 1. Weight-related comorbidities (i.e., type 2 diabetes, dyslipidaemia, hypertension)
 - 2. Neuropsychiatric conditions (mania, bipolar disorder, major depressive disorder [MDD], anorexia nervosa, bulimia)
 - 3. Uncontrolled hypertension
 - 4. Moderate or severe renal impairment
 - 5. End-stage renal disease
 - 6. Seizure disorder
 - 7. Hepatic impairment (defined by Child-Pugh score category)
 - 8. Central nervous system tumour
- 4. Concomitant medication use, including: naltrexone, bupropion, CYP2B6 inhibitors, CYP2B6 inducers, CYP2B6 substrates, CYP2D6 substrates, drugs that lower seizure threshold, opioid or opiate agonist, or MAOI (obtained via ATC [outpatient, Nordic data] or NDC [US data])
- 5. Pregnancy status and breastfeeding status (obtained via ICD-10 codes)
- 6. AESIs (obtained via ICD-10 codes):
 - 1. Seizures

- 2. Suicidality (i.e., suicidal ideation, attempted suicide or completed suicide)
- 3. Neuropsychiatric events (i.e., mania or depression)
- 4. Hepatotoxicity
- 5. Severe hypersensitivity reaction

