9.3.3. Covariates

When available, the following variables needed to conduct analysis for the primary and secondary research objectives will be collected. Variable availability from each country will be summarized in the SAP and is included in Appendix 3 in draft form.

Demographics and Baseline variables (Within 365 days before index date unless otherwise stated below; as depicted in Figure 1):

- 9. Patient demographics (age and sex on index date) (obtained directly from data source)
- 10. BMI, height, weight (most recent value on or before the index date) (obtained directly from data sources; BMI may be calculated if height and weight available)
- 11. Relevant comorbidities (obtained via ICD-10 codes), including:
 - 1. Weight-related comorbidities (i.e, type 2 diabetes, dyslipidaemia, hypertension)
 - 2. Neuropsychiatric conditions (mania, bipolar disorder, major depressive disorder [MDD], anorexia nervosa, bulimia)
 - 3. Uncontrolled hypertension, if possible
 - 4. Moderate or severe renal impairment
 - 5. End-stage renal disease
 - 6. Seizure disorder
 - 7. Hepatic impairment (defined by Child-Pugh score category, if available)
 - 8. Central nervous system tumour

- 12. History of, or current substance abuse/dependencies including acute opiate withdrawal (obtained via ICD-10 codes)
- 13. History of uncontrolled hypertension, seizures, bipolar disorder, MDD, anorexia nervosa, or bulimia (obtained via ICD-10 codes)
- 14. Prior medication use, including: naltrexone, bupropion, CYP2B6 inhibitors, CYP2B6 inducers, CYP2B6 substrates, CYP2D6 substrates, Monoamine oxidase inhibitors, Opioids, Opium alkaloids and derivatives and drugs that lower seizure threshold (obtained via ATC [Nordic data] or NDC [US data]) see Appendix 2 and 2A
- 15. Pregnancy status and breastfeeding status (obtained via ICD-10 codes)

All variables will be identified from the data sources outlined below using a pre-specified list of definitions per database (Appendix 3), to be defined in the SAP as final.

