9.7.3.1. Incidence Rates of AESIs in Subgroups of Patients

If data are available and appropriate predictors are available in the respective database, sensitivity analyses around the definition of each type of AESI will be performed. Incidence proportion and density of each type of AESI will also be calculated for the subgroup of patients compliant or non-compliant with the EU SmPC (as listed in section 9.7.1, the criteria will be adapted for the relevant country of the data source stems if the SmPC differ across such countries, i.e., for U.S.), including relevant comorbidities, concomitant medications, and pregnancy. Adaptations will be made if BMI is not available; these will be described in the SAP. The incidence rate (and 95% CI) of new onset comorbidities and concomitant medication after initiation of Mysimba/Contrave will be assessed. Incidence rates will be determined both for the person-years of time exposed to Mysimba/Contrave (i.e., while patient taking medication) after the index date as well as for all person time through 548 days after the index Mysimba/Contrave prescription.

The incidence rate (and 95% CI) of pregnancy and breastfeeding after the Mysimba/Contrave index date will be assessed among females initiating Mysimba/Contrave. These analyses will be conducted in data sources where the necessary variables are present.

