Name of the main author of the protocol.				
Name of the main author of the protocol:				
Date: dd/Month/year				
Signature:				

15. Appendix 2. Code lists

Mysimba ATC: A08AA62 Contrave NDC: search terms – Contrave, naltrexone, bupropion Naltrexone ATC: N07BB04, A06AH01, N02AA56	
Contrave NDC: search terms – Contrave, naltrexone, bupropion	
Naltrexone ATC: N07BB04, A06AH01, N02AA56	
NDC: search terms – naltrexone	
Bupropion ATC: N06AX12	
NDC: search terms – bupropion	
Concomitant Medications	
CYP2B6 inhibitors See Appendix 2A	
CYP2B6 inducers See Appendix 2A	
CYP2B6 substrates See Appendix 2A	
CYP2D6 substrates See Appendix 2A	
Drugs that lower Propoxyphene, remifentanil, sufentanil, tapentadol, tramadol,	
seizure threshold baclofen, buspirone, dalfampridine, lithium, mefenamic acid,	
amphetamine, benzphetamine hydrocholoride, dextroamphetan	mine,
hydroxyamphetamine hydrobromide, lisdexamfetamine dimes	
methamphetamine hydrochloride, cocaine, phenylpropanolam	
dexamphetamine, methylphenidate	
Opioid or opiate ATC: N02A;	
agonist	
Opium alkaloids & ATC: R05DA, N02AA	
derivatives	
MAOI ATC: N04BD, N06AF, N06AG	
Seizures ICD-10: G40	
Increase in blood ICD-10: R00.0, R03.0	
pressure or heart rate	
Hypersensitivity, ICD-10: T78, L51	
including Stevens-	
Johnson	
Serotonin syndrome ICD-10: T43.225A	
Suicidality ICD-10: R45.851, T14.91	
Diabetes ICD-10: E10-E11	
Dyslipidaemia ICD-10: E78	
Neuropsychiatric	
conditions:	
Mania ICD-10: F30	
Bipolar disorder ICD-10: F31	

N4 : 1 :	ICD 10 F22
Major depressive	ICD-10: F33
disorder	ICD 10 F50 0
Anorexia nervosa	ICD-10: F50.0
Bulimia	ICD-10: F50.2
Hypertension	ICD-10: I10-I16
TT . 11 1	
Uncontrolled	ICD-10: I10-I16 (with Systolic ≥140 mmHg or diastolic ≥90 mmHg)
hypertension	10D 10 N10 0 N10 5
Moderate or severe	ICD-10: N18.3-N18.5
renal impairment	
End stage renal	ICD-10: N18.6
disease	
Hepatic impairment	ICD-10: K70, K72-K75
Central nervous	ICD-10: C72
system tumour	
Substance	ICD-10: F10-F19
abuse/dependency	
	ATC: N06AA11
Protriptyline*	NDC: search terms – protriptyline
Dannanidal (Anarril)*	ATC: N05AD07
Benperidol (Anquil)*	No NDC
Flupentixol	ATC N05AF01
(Depixol)*	No NDC
Fluphenazine	ATC: N05AF02
(Modecate,	NDC: search terms – fluphenazine
Prolixin)*	•
Levomepromazine	ATC: N05AA02
(Nozinan)*	No NDC
Loxapine	ATC: N05AH01
(Loxitane)*	NDC: search terms – loxapine
	ATC: N05AE02
Molindone (Moban)*	NDC: search terms – molindone
	ATC: N05AC01
Periciazine*	No NDC
Sulpiride (Dolmatil,	ATC: N05AL01
Sulpor)*	No NDC

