Thiothixene	ATC: NONE IDENTIFIED
(Navane)*	NDC: search terms – thiothixene
	ATC: N05AB06
Trifluoperazine (Stelazine)*	NDC: search terms – trifluoperazine
(Stefazifie).	
Amisulpride (Solian)	ATC: N05AL05
	NDC: search terms – amisulpride
Geodon	ATC: N05AE04
(ziprasidone)*	NDC: search terms – ziprasidone

Olanzapine	ATC: N05AH03
(Zyprexa)	NDC: search terms – olanzapine
Isocarboxazid	ATC: N06AF01
(Marplan)*	NDC: search terms – isocarboxazid
(Iviaipiaii)	ATC: N06AF03
Phenelzine (Nardil)*	NDC: search terms – phenelzine
Tranylcypromine	ATC: N06AF04
(Parnate)*	NDC: search terms – tranylcypromine
A 1 11 11	ATC: L01EM03
Alpelisib	NDC: search terms – alpelisib
	ATC: N06BA13
Armodafinil	NDC: search terms – armodafinil
	ATC: C10AA05
Atorvastatin	NDC: search terms – atorvastatin
	ATC: NONE IDENTIFIED
Avacopan	NDC: search terms – avacopan
	ATC: A07EA04, C05AA05, D07AC01, D07XC01, H02AB01,
	R01AD06, R03AD04, S01BA06, S01CB04, S02BA07, S03BA03
Betamethasone	NDC: search terms – betamethasone
	ATC: A07EA06, D07AC09, R01AD05, R03BA02
Budesonide	NDC: search terms – budesonide
	ATC: C10AA06
Cerivastatin	No NDC
	ATC: A01AC02, C05AA09, D07AB19, D07XB05, D10AA03,
	H02AB02, R01AD03, S01BA01, S01CB01, S02BA06, S03BA01
Dexamethasone	NDC: search terms – dexamethasone
	ATC: N03AB05
Fosphenytoin	NDC: search terms – fosphenytoin
	ATC: A01AC03, A07EA02, C05AA01, D07AA02, D07XA01,
	H02AB09, S01BA02, S01CB03, S02BA01, D07AC16
Hydrocortisone	NDC: search terms – hydrocortisone
,	ATC: L01EM01
Idelalisib	NDC: search terms – idelalisib
	ATC: J02AC05
Isavuconazole	No NDC
	ATC: N01AB06
Isoflurane	NDC: search terms – isoflurane
	ATC: L01XX62
Ivosidenib	NDC: search terms – ivosidenib
	ATC: N05CM21
Lemborexant	NDC: search terms – lemborexant
	ATC: L01ED05
Lorlatinib	NDC: search terms – lorlatinib
Loriumiio	ATC: R07AX30 (with Ivacaftor)
Lumacaftor	NDC: search terms – lumacaftor
Lumavanton	1 M.C. Scarcii terriis — rumacartor

	ATC: N02BB02
Metamizole	No NDC
TVICKIIII ZOIC	ATC: D07AA01, D10AA02, H02AB04, D07AC14
Methylprednisolone	NDC: search terms- methylprednisolone
Tribuny iprodume orono	ATC: L01EX10
Midostaurin	NDC: search terms- rydapt
THEOSEASTII	ATC: None Identified
Mitapivat	NDC: search terms- mitapivat
- Trittapi vat	ATC: N06BA07
Modafinil	NDC: search terms- modafinil
Wodaniiii	ATC: C08CA04
Nicardipine	NDC: search terms- nicardipine
Titearaipine	ATC: L01EA03
Nilotinib	NDC: search terms- nilotinib
TVIIOTIIIO	ATC: L01XK01
Olaparib	NDC: search terms- olaparib
Оприно	ATC: N03AX22

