Perampanel	NDC: search terms- perampanel
1 Clampaner	ATC: P03AC04, P03AC54
Permethrin	NDC: search terms- permethrin
1 crimetiniii	ATC: L01EX15
Pexidartinib	NDC: search terms- pexidartinib
1 CAIGGITHIIO	ATC: N03AA02
Phenobarbital	NDC: search terms- phenobarbital
1 Henoodi ottai	ATC: N07XX11
Pitolisant	NDC: search terms- pitolisant
1 Honsant	ATC: A07EA01, C05AA04, D07AA03, D07XA02, H02AB06,
	H02AB06, R01AD02, S01BA04, S01CB02, S02BA03, S03BA02,
	D07CA03, S01CA02, S02CA01, S03CA02, D07BA01,
	S01BB02
	V03AB05, A01AC54, R01AD52
Prednisolone	NDC: search terms- prednisolone
	ATC: A07EA03, H02AB07
Prednisone	NDC: search terms- prednisone
110011111111111111111111111111111111111	ATC: L02BX04, H01CC54
Relugolix	NDC: search terms- relugolix
	ATC: A02BD16, J04AB04
Rifabutin	NDC: search terms- rifabutin
	ATC: J04AB02, J04AM02, J04AM07, J04AM05, J04AM06
Rifampicin	No NDC
	ATC: J04AB05
Rifapentine	NDC: search terms- rifapentine
	ATC: 10BD04, A10BD03, A10BG02
Rosiglitazone	No NDC
Sotorasib	ATC: L01XX73
501014510	1110. D01/M1/J

	NDC: search terms- sotorasib
	ATC: M04AB02
Sulfinpyrazone	No NDC
1 7	ATC: B01AC24
Ticagrelor	NDC: search terms- ticagrelor
 	ATC: A10BG01
Troglitazone	No NDC
	ATC: L01EC01
Vemurafenib	NDC: search terms- vemurafenib
	ATC: P03AX07
Abametapir	NDC: search terms- abametapir
•	ATC: L01EF03
Abemaciclib	NDC: search terms- abemaciclib
	ATC: J05AB17
Brincidofovir	No NDC
	ATC: L01XA01
Cisplatin	NDC: search terms- cisplatin
	ATC: D10AX06
Clascoterone	NDC: search terms- clascoterone
	ATC: A01AB18, D01AC01, G01AF02
Clotrimazole	NDC: search terms – clotrimazole
	ATC: M04AC01
Colchicine	NDC: search terms- colchicine
	ATC: D11AH06
Crisaborole	NDC: search terms- crisaborole
	ATC: L01ED01
Crizotinib	NDC: search terms- crizotinib
	No ATC
Curcumin	NDC: search terms- curcumin
	ATC: L01EC02
Dabrafenib	NDC: search terms- dabrafenib
	ATC: LO1DB01
Doxorubicin	NDC: search terms- doxorubicin
	ATC: A04AD10
Dronabinol	NDC: search terms- dronabinol
	ATC: R07AX32
Elexacaftor	NDC: search terms- elexacaftor
	ATC: L02BB04
Enzalutamide	NDC: search terms- enzalutamide
	ATC: D08AX08, V03AB16, V03AZ01
Ethanol	NDC: search terms- ethanol
	ATC: P01CA03
Fexinidazole	NDC: search terms- fexinidazole
	ATC: J02AC02
Itraconazole	NDC: search terms- itraconazole

	ATC: D01AC08, G01AF11, H02CA03, J02AB02
Ketoconazole	NDC: search terms- ketoconazole
Retocoliazoic	ATC: L01EX08
Lenvatinib	NDC: search terms- lenvatinib
Lenvamino	NO ATC
Levoketoconazole	NDC: search terms- levoketoconazole

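### The CYP2B6/CYP2D6 code lists have no route restriction and no rule for 12 drugs listed as both inhibitor and inducer, so the CYP medication flags misclassify users of locally acting products and overlap

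*Protocol*

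**What the plan says.** Section 9.3.2 collects, after the index date, "Concomitant medication use, including: naltrexone, bupropion, CYP2B6 inhibitors, CYP2B6 inducers, CYP2B6 substrates, CYP2D6 substrates, drugs that lower seizure threshold". Section 9.3.3 collects the same groups at baseline: "Prior medication use, including: naltrexone, bupropion, CYP2B6 inhibitors, CYP2B6 inducers, CYP2B6 substrates, CYP2D6 substrates". Section 9.3.2 also says that variables are identified from a pre-specified code list and points to Appendix 2.

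Appendix 2 passes group membership on, for example "CYP2B6 inhibitors See Appendix 2A", and Appendix 2a lists drug names in columns without route. The codes for each drug are back in Appendix 2. Hydrocortisone, in the inducer column, has "ATC: A01AC03, A07EA02, C05AA01, D07AA02, D07XA01", continued as "H02AB09, S01BA02, S01CB03, S02BA01, D07AC16". Clotrimazole, in both the inhibitor and the inducer column, has "ATC: A01AB18, D01AC01, G01AF02". The NDC searches use the ingredient name.

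Section 9.7.3.1 plans incidence rates of newly started concomitant medication. It also plans AESI incidence in the SmPC-compliance subgroups, "including relevant comorbidities, concomitant medications, and pregnancy".

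**The concern.** Sorting co-medication into inhibitors, inducers and substrates is informative only if a flag marks a drug that reaches the circulation and if the groups can be told apart. As the lists stand, a first dispensing of hydrocortisone cream counts as new CYP2B6 inducer use. A clotrimazole vaginal product counts as both inhibitor and inducer use. A reader of the tables would take the frequency of CYP-interacting co-medication to be higher than it is, and the inhibitor and inducer rows would partly describe the same patients.

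**Working it through.** The protocol gives no figure of its own to reproduce here. The check is a count of the codes and a comparison of two columns.

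**Inputs.** ATC codes per drug come from Appendix 2, and column membership from Appendix 2a. The reading of the ATC prefixes is that of the classification itself and is not spelled out in the protocol: D skin; S eye and ear; R01 nasal; A01 mouth; C05 haemorrhoidal; G01 vaginal; A07 intestinal; R03 inhaled or other airway; H02 systemic corticosteroid.

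**Step 1: codes for five listed agents.**

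| Agent | Codes | H02 | D or S | R01, A01, C05, G01 | A07 or R03 |
|---|---|---|---|---|---|
| Betamethasone | 11 | 1 | 6 | 2 | 2 |
| Budesonide | 4 | 0 | 1 | 1 | 2 |
| Dexamethasone | 11 | 1 | 7 | 3 | 0 |
| Hydrocortisone | 10 | 1 | 6 | 2 | 1 |
| Clotrimazole | 3 | 0 | 1 | 2 | 0 |
| Total | 39 | 3 | 21 | 10 | 5 |

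The row totals agree: 3 + 21 + 10 + 5 = 39.

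**Step 2: is this confined to those five?** No. Adding methylprednisolone, prednisolone and prednisone to the four corticosteroids above gives 61 unique codes, of which 54 are in local, intestinal or inhaled groups (10 + 10 + 4 + 9 + 3 + 17 + 1, in the order betamethasone, dexamethasone, budesonide, hydrocortisone, methylprednisolone, prednisolone, prednisone). Among other listed drugs the local codes are 6 of 7 for miconazole, 4 of 5 for rifamycin and 2 of 5 for timolol. Clascoterone and crisaborole, both in the inhibitor column, have a dermatological code only (D10AX06, D11AH06).

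**Step 3: overlap of the CYP2B6 columns.** The inhibitor column has 69 legible names and the inducer column 69. Their intersection has 12: cenobamate, clotrimazole, dabrafenib, enasidenib, fexinidazole, medical cannabis, modafinil, pexidartinib, rifamycin, ritonavir, simvastatin and sorafenib. Simvastatin is also in the CYP2D6 column, so one dispensing sets three flags. One row of the inhibitor column appears damaged by text extraction. The missing name is probably methimazole, which has a code entry in Appendix 2 but is not in the inducer column, so the 12 stand.

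**Step 4: where the flags go.** They enter the baseline medication description (9.3.3), the post-index medication variables (9.3.2), and the incidence of new concomitant medication and any AESI tabulation by concomitant medication (9.7.3.1). They do not enter the SmPC criteria in Sections 8 and 9.7.2, whose medication items are bupropion, naltrexone, MAOIs and opioids.

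**Step 5: size in patients.** This cannot be computed. Codes are not dispensings, and the protocol gives no dispensing counts by product.

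**The case against.** The strongest reply is that these are descriptive medication variables. The protocol names no CYP interaction subgroup and does not say that the groups identify patients with altered drug exposure. The reference to concomitant medications in Section 9.7.3.1 is generic. The groups for the increased-risk objective in Section 8 are all users, compliant users and non-compliant users. All of this stands.

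Three stronger readings are therefore tempting but unsupported.

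- A reader might infer that the CYP groups fail altogether to identify interacting users. They also contain many systemic codes, so they mix the two kinds of user.
- A reader might infer that topical steroids and statins dominate the groups and pull a true rate ratio towards 1. That needs prevalences the document does not give. Statins are systemic drugs and do not illustrate the route problem. Item 3.4 of the ENCePP checklist says that no measure of association is specified.
- A reader might take dual listing as an error in itself. A drug can be listed for both properties, and the protocol does not say the groups are exclusive. The gap is the missing reporting rule.

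It can also be said that Section 9.3.3 leaves final definitions per database to the SAP. This softens the point without removing it, because Section 9.3.2 makes Appendix 2 the pre-specified code list, and the local codes are written there. Product-level exclusions were evidently possible: the clonidine NDC search excludes apraclonidine.

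**Conclusion.** The point holds as a misclassification and overlap of the CYP medication flags. Appendix 2 counts locally acting products as CYP-interacting medication, and 12 drugs fall in both CYP2B6 groups with no rule for reporting them. For the five agents examined, 36 of 39 codes (39 − 3) lie outside the systemic corticosteroid group, and 21 are skin or eye/ear codes. These agents were chosen as clear examples, so the proportion does not describe the whole list. The conclusion rests on the usual meaning of the ATC prefixes and on the columns of Appendix 2a as extracted.

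The consequence is limited. The CYP rows of the baseline and follow-up tables, the incidence of new CYP-interacting medication, and any AESI tabulation by these flags would be hard to interpret as labelled. The SmPC-compliance classification, and the AESI comparison built on it, do not depend on these lists.

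**What to change.** In Appendix 2, restrict the CYP lists to systemic-route codes:

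- Remove the D, S, R01, A01, C05 and G01 codes of locally acting products.
- Review the A07 and R03 codes one by one and record the decision for each.
- Apply a matching route filter to the NDC searches.

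For the five agents tabulated, this removes 31 codes (21 + 10), sends 5 to review and keeps 3.

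Report users of the dual-listed drugs as a separate category, inhibitor and inducer, instead of counting them in both groups without comment. Clotrimazole would leave this category in the ATC-coded data, since all three of its codes go. The broad list may be kept as a descriptive sensitivity table.

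The cost is an edit to a code list; no new data are needed. The CYP groups become smaller and their rates less precise.
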